We added a brief (3-minute) word recognition memory task to our neuropsychological assessments to investigate if differences exist between those who attempt suicide vs. those that do not, as previous studies have suggested. Additionally, we modified treatment delivery requirements to allow for outpatient individual sessions if necessary, as many eligible Veterans have brief inpatient stays.

The following amendments were made after the first participants had enrolled:

3. 1-24-14:

We expanded inclusion criteria for our study to include Veterans who have current and active high risk for suicide flags who are either currently hospitalized without current suicidal ideation or who had mental health related hospital treatment within the past month. Next, we changed our Time 2 and Time 3 assessments to line up with mid and post-treatment, respectively, rather than with a fixed time point. to allow us to better support our research hypotheses as each participant will have received the appropriate number of treatment sessions prior to their mid and post treatment assessments. Control subjects will be matched with treatments participants in blocks according to date of consent and group start date so that the assessment timeline is consistent between treatment and control subjects.

4. 2-21-14:

We requested to record the C-SSRS assessment with explicit informed consent of the subject so that it can be rated by a blind rater in order to eliminate potential bias and ensure continuous interrater reliability.

5. 4-14-14:

We detailed our procedures for contacting Veterans enrolled in the study for both treatment sessions and assessment appointments, explicitly noting that we will use both letters and telephone calls to outreach subjects. Our research team utilizes an approach congruent with standard VA NJ mental health care and VA Suicide Prevention Coordinators to maintain engagement with a person-centered, relationship-building approach.

6. 5-8-14:

We revised inclusion criteria so that a high risk for suicide flag is not a requirement for participation as some Veterans present with suicide risk yet are not administratively flagged by Suicide Prevention.

7. 5-20-14:

[name]. will assume the role of Principal Investigator as [name]., is retiring as of May 30, 2014.

8. 7-22-14:

We expanded inclusion criteria to include Veterans treated in outpatient programs. We have formulated the criteria to maintain a focus on a sample that has a suicide event or "crisis" and shows recent risk of suicide behavior.

9. 10-6-14:

We are specifying all methods the study team may use to recruit Veterans receiving services as outpatients at VA NJ, including mailing letters prior to calling, direct referrals by providers, and the ability for interested referred Veterans to contact the study team directly.

10. 12-5-14:

We propose to offer the mindfulness-based cognitive therapy to control subjects after they have completed one year of study participation. We are also requesting that these veterans receive reimbursement for travel expenses at a rate of .415/mile for treatment group attendance.

11. 6-26-16:

We added an optional, qualitative assessment for treatment subjects who completed the study to identify common patterns across cases within each category (e.g., positive response, negative response, unengaged).

12. 7-25-17:

We added a statement to our consent form to address an expected risk, discomfort, or inconvenience of taking part in study: "Because the treatment sessions focus on helping you to deal with some of the difficulties you are having, you may feel distressed or unsettled during a treatment session. If you are feeling unsettled, please let your instructor know so he or she can counsel you." While we recently conducted an analysis of this issue and found low occurrence rates, we felt it prudent to outline in the informed consent document that feeling upset during therapy is natural. Additionally, we clarified language in our study protocol to include licensing information for study staff and clinicians and outline a more detailed and refined protocol for managing emergent suicidal risk.

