Potential confounds that are known at baseline will be controlled for using the urn randomization method. This method balances the randomization based on predetermined indicators that could affect the outcome. Using this procedure, we will block the randomization according to: presence or absence of psychosis (either a psychotic diagnosis or one that includes psychotic features vs. no psychosis); and previous number of suicide attempts (none vs. 1+). Our randomized block design will thus classify participants into one of 4 blocks based on diagnosis (2 categories) and previous attempts (2 categories). We selected these variables in order to insure a balanced distribution of patient characteristics that might have effects on treatment engagement and/or outcomes.

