3.3 Sample Size Justification & Subject Selection

The study will enroll a total of 164 subjects hospitalized on the **second** and **second** acute psychiatric units who qualify for inclusion on the VA's High Risk for Suicide List (HRSL). The study will only sample HRSL patients who experienced a hospitalization as a result of their index suicide event, which represents approximately 77% of all active HRSL patients. Approximately 8-10 patients are admitted to the acute units for suicide risk monthly. Over an approximately 36-month recruitment period, we expect to recruit approximately 3-5 patients per month to meet our enrollment goal.

Because our inclusion criteria are broad, we expect our sample to be representative of the population of HRSL patients hospitalized on the acute units. In FY 2011, this population was 85% male, 52% Caucasian; 33% Black; 8% Latino; and 4% Asian. The mean age was 47 (range=23 to 95). These veterans were diverse in terms of psychiatric diagnoses (non-mutually exclusive diagnoses include Depression-60%; PTSD-47%; Drug-related disorders-40%; Alcohol-Related disorders-38%; Bipolar Disorder-20%; and Schizophrenia-9%) and service era (Vietnam Era-29%; Post-Vietnam-25%; Gulf War-13%; OEF-OIF-25%).

To detect group differences on our principal measure, duration of time to first suicide event, we based our power analysis on prior literature and pilot data. Using the stpower cox command in Stata/MP 12.1 for Windows, which follows Hsieh and Lavori, ⁴ our power analysis estimated the required sample size to achieve 80% power at a 0.05 alpha level at a pre-attrition recruitment of 164 participants evenly

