randomized at a 1:1 ratio to 82 per group. Based on our pilot data we assumed a hazard ratio of 0.421 and a control group failure probability of 32.1%; based on a comparable study by Brown et al., which reported an 18% attrition rate at 12 months, we assumed a 20% attrition rate, and used the standard deviation of the covariate of interest, group assignment, of 0.5. As noted, this analysis indicates we will need to recruit 82 subjects per group (total n=164) to attain a sample size of 66 per group (total n=132) after attrition. Moreover, we expect the study will be powered sufficiently to demonstrate clinical significance of the intervention as well. With respect to our main outcome measure, "duration of time to first suicide event," for example, our pilot data indicate the intervention may reduce by more than half the likelihood of a second suicide event within 12 months. This would translate into substantial savings in both human suffering and hospitalization costs.

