MBCT-S is designed to achieve a transitional model via its session structure, which involves two individual sessions in the inpatient setting and 6 group outpatient sessions. We expect MBCT-S to promote continuity between inpatient and outpatient treatment phases by establishing a therapeutic alliance prior to the inpatient-outpatient transition that will be relied upon to improve outpatient engagement. The first 2 individual inpatient sessions are geared to introducing the patient to the program and the basic concepts of mindfulness, reviewing each patient's personal Safety Plan, enhancing the identification of suicide triggers identified on the Safety Plan, introducing the application of mindful awareness of suicide triggers and providing personalized guidance on establishing a home practice. The remaining group outpatient sessions are devoted to enhancing the ability to apply mindfulness to the thoughts, feelings and situations likely to trigger suicidal thinking.

MBCT-S adopts a patient-centered model in a number of ways. Unlike purely group-based approaches, MBCT-S's initial use of individual sessions provides a phase where the treatment rationale and goals can be individualized. This will rely heavily on tying the treatment to the Suicide Safety Plan, which is itself highly individualized. Patient-centeredness is also achieved through a design that is compatible with the population's needs and preferences. The VA's own data show that veterans at risk of suicide demonstrate significant difficulty engaging with treatments that are long-term and of high intensity, with no VISNs meeting the annual high risk suicide performance monitor for required mental health visits as of October, 2011. Thus, MBCT-S, which is shorter term and partially completed prior to discharge, was in part selected to better match the treatment utilization patterns of this population. Moreover, the intervention was specifically designed to address the challenge of outpatient continuity among patients with a myriad of presenting problems. Achieving this type of continuity requires an engagement-oriented approach that emphasizes patient support.

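### Eligibility was widened beyond inpatients after enrolment began, but entry setting is absent from the listed baseline comparison and the Cox models: a small, cheap gap in precision and reporting

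*Combined protocol and SAP*

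**What the plan says.** **Who enters.** Section 3.4.1 requires current treatment on one of the two acute psychiatric units. The Protocol Amendments list then records changes made after enrolment had begun. Item 3 (1-24-14) admits flagged Veterans who are "currently hospitalized without current suicidal ideation or who had mental health related hospital treatment within the past month". Item 6 (5-8-14) drops the flag requirement. Item 8 (7-22-14) reads: "We expanded inclusion criteria to include Veterans treated in outpatient programs". It adds that the criteria keep the focus on people with a suicide event or crisis and recent risk.

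**Allocation.** Section 3 forms four blocks from psychosis and previous attempts, chosen to "insure a balanced distribution of patient characteristics that might have effects on treatment engagement and/or outcomes". The only listed change of method is the move to Excel, made before recruitment. Item 3 also matches controls to treated participants by consent date and group start date, for assessment timing.

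**Baseline comparison.** Section 5 lists demographics, previous attempts, diagnosis and service era. Variables that differ at p < .10 become covariates.

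**Models.** For H1a, Section 5 specifies a Cox model with group, site and a partially nested therapist effect; H2a is similar. Site means campus (Section 3.2), not care setting.

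**Intervention.** Section 4.1 describes two individual inpatient sessions followed by outpatient groups, with the aim of "establishing a therapeutic alliance prior to the inpatient-outpatient transition that will be relied upon to improve outpatient engagement". Before recruitment, the second listed amendment already allowed the individual sessions to be given to outpatients, because inpatient stays are often brief.

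**The concern.** The amended trial can contain three kinds of entrant: current inpatients, people discharged within the past month, and outpatients. Time to first event runs from baseline for all of them, but baseline falls at different points in their care. An inpatient still has discharge ahead. A recently discharged entrant has used part of the 90 days of enhanced care that Section 4.1 counts from discharge. It is therefore reasonable to expect that setting may predict the event rate, although the documents give no figures by setting.

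A plausible prognostic factor known at consent would normally be tabulated by arm and put in the model by pre-specification. Here the eligibility change is recorded without a matching change to the analysis. Three things are at stake:
- a chance difference between arms in the share of inpatient entrants would go unadjusted;
- a little precision would be lost;
- if the treatment works less well outside the inpatient pathway, the pooled estimate would be diluted and no planned output would show it.

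**Working it through.** **1. Reproduce the plan's sample size.** Section 3.3 gives the inputs: "sample size to achieve 80% power at a 0.05 alpha level at a pre-attrition recruitment of 164 participants"; "we assumed a hazard ratio of 0.421 and a control group failure probability of 32.1" per cent; "used the standard deviation of the covariate of interest, group assignment, of 0.5"; "randomized at a 1:1 ratio to 82 per group"; and 20% attrition. Sidedness is not stated; two-sided reproduces the figure.
- Events = (1.960 + 0.842)² / (0.5² × ln(0.421)²) = 41.95, so 42.
- Participants = 41.95 / 0.321 = 130.7, so 131 (the plan has 132).
- After attrition: 131 / 0.80 = 163.75, so 164, as stated.
- Power at 132 × 0.321 = 42.4 events is 80.4%.

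This works with 32.1% applied to the whole sample, and I use it that way below. Nothing in the calculation depends on setting, so stratifying by setting leaves 42 events and 164 participants unchanged.

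**2. Size of a chance imbalance.** The share p of non-inpatient entrants is not given; I assume 20-50%. The SD of the between-arm difference in that share is sqrt(4p(1−p)/164):
- p = 0.2: 0.062
- p = 0.3: 0.072
- p = 0.5: 0.078

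At p = 0.5 the 95% range is about ±15 points, and a gap above 10 points has a probability of 20%. Blocking on psychosis and previous attempts balances setting only so far as setting is correlated with them.

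**3. Effect on the hazard ratio.** Let h be the non-inpatient hazard relative to inpatients (assumed 0.33-0.5). A k-SD imbalance multiplies the estimated HR by about exp(k × SD × |ln h|), in either direction.
- k = 1: from exp(0.062 × 0.693) = 1.04 to exp(0.078 × 1.109) = 1.09.
- k = 2: from 1.09 to 1.19.

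A direct check at p = 0.5 and h = 0.5, with shares of 55% and 45%: (0.45 + 0.55 × 0.5) / (0.55 + 0.45 × 0.5) = 0.725 / 0.775 = 0.94. An HR of 0.421 would then read about 0.39. With h = 2 the ratio is 1.55 / 1.45 = 1.07, and 0.421 would read about 0.45.

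For scale, the standard error of log HR at 42 events is 2/√42 = 0.31. The 1-SD shift on the log scale is 0.043 to 0.087, or 14-28% of that.

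**4. Does pooling damage the test?** Simulation used 66 per arm, 12 months, 50% outpatients (assumed), 4,000 runs per scenario, and an unstratified versus a setting-stratified Cox model.

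| Scenario | Unstratified | Stratified |
|---|---|---|
| Power, HR 0.421, outpatient hazard 0.5× | 63.7% | 64.5% |
| Power, HR 0.421, equal hazards | 76.4% | 76.5% |
| Power, HR 0.421, outpatient hazard 2× | 87.7% | 89.7% |

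Under the null, rejection rates were 3.5-5.3% in all analyses. Stratifying gains about 1-2 points when setting matters and costs nothing when it does not. Simulated power runs below the formula (76.4% against 80.4% with equal hazards), so compare the columns rather than the levels.

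**5. What pooling could hide.** These are formula figures, all under assumed inputs.
- *Changed event rate, same HR.* With outpatient hazard at half the inpatient value, power is 75.6% (25% outpatients) or 69.8% (50%). With double the hazard it is 86.1% or 90.3%.
- *Weaker effect in outpatients.* Pooled ln HR = 0.5 ln(0.421) + 0.5 ln(HR in outpatients). Outpatient HRs of 0.6, 0.8 and 1.0 give pooled HRs of 0.50, 0.58 and 0.65, and power of 61%, 43% and 29% at 42.4 events.

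These are consequences of who was enrolled. Adding setting to the model does not recover the lost power; it only makes the cause visible.

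**6. Precision by setting.** With equal hazards, 42.4 events split into about 21 per setting at a 50% share, or about 11 among non-inpatients at 25%. The 95% limits for a setting-specific HR are then the estimate multiplied and divided by exp(1.96 × 2/√21.2) = 2.3, or exp(1.96 × 2/√10.6) = 3.3.

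**The case against.** The case for leaving the plan alone has real substance.

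- **Randomisation protects the comparison.** Setting is balanced in expectation, and chance imbalance is already part of the standard error. This stands. A reader might infer that pooling settings biases the treatment effect or invalidates the Cox test; step 4 shows no inflation of type I error.
- **Different hazards are not documented.** A reader might take it as established that the new entrants have a different event rate. No rate by setting is given, and amendment 8 says that the criteria keep a focus on recent crisis. This stands, and is why every magnitude above is conditional.
- **Variation in delivery came first.** A reader might infer that admitting outpatients created a second form of MBCT-S. Outpatient individual sessions were already allowed before recruitment, for inpatients with short stays. This stands: entry setting does not identify who received inpatient sessions.
- **Section 4.1 does not call setting prognostic.** Its remark on alliance and engagement says how the sessions are meant to work in the treated arm. This stands; the prognostic argument rests on plausibility.
- **Existing provisions may cover it.** Section 5 aims to find any baseline difference that could bias results, and Section 3.5 collects inpatient treatment episodes. This stands in part. The data will be there, but the list omits setting, and the p < .10 rule makes adjustment depend on the observed imbalance.
- **The body text predates the amendments and the list is a summary.** Silence is therefore limited evidence of later practice. That is fair, but neither source records any adjustment for setting. The point is that omission, not a mismatch between the two texts.

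**Conclusion.** The concern holds in a limited form. Eligibility was extended to recently discharged Veterans and outpatients after enrolment began. Entry setting appears neither in the listed baseline comparison nor in the H1a and H2a models.

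The consequence is modest: a typical chance imbalance shifts the HR by a factor of about 1.04-1.09, and about 1-2 points of power are forgone. Both rest on assumed shares and hazards. The larger possible exposure, dilution among non-inpatient entrants, comes from the enrolled mix rather than from the missing term. The omission matters there only because the planned outputs would not reveal it.

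Two further inferences are not supported. One is that randomisation needs a new stratum. That would help only remaining entrants; the amendment list runs three years past amendment 8, against a planned recruitment of about three years, and adjustment in the analysis achieves nearly the same. The other is that the transitional-model claim should be confined to inpatient entrants, since some of them may have had their individual sessions as outpatients.

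This is a low-cost improvement, not a threat to the validity of the primary test.

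**What to change.** Before unblinding, amend Section 5 as follows:

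1. Define entry setting at consent in two levels, inpatient versus other, and add it to the baseline comparison.
2. Stratify the H1a and H2a Cox models by it, and enter it as a fixed term in the H1b and ideation models, whatever the p < .10 screen shows.
3. Report the treatment effect by setting with confidence intervals, labelled descriptive because each subgroup will have few events.
4. Record where each participant's individual sessions were given, and tie any statement about the inpatient-to-outpatient model to that record rather than to entry setting.

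The cost is SAP wording and one derived variable; setting is already known at screening. The sample size does not change. The drawback is slightly sparser strata, which two levels keep small.
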